5.6 Blinding, Emergency Envelopes and Breaking the Study Blind

Not applicable for this open-label study.

5.7 Treatment Compliance

5.7.1 Drug Dispensing and Accountability

All IMP provided to the site will be accounted for. This includes IMP received at the site, dispensed to patients, and IMP returned unused by the subject/patient.

Sponsor or designee will deliver Octanorm to the participating investigators. Investigator will keep current drug inventory and dispensing log, detailing the dates, batch (lot) numbers, and quantities of IMP received and dispensed to each patient and the remaining quantity.

The inventory and drug dispensing log will be available to the monitor to verify drug accountability during the study. The study monitor will review all empty and partially used vials of IMP and will cross-check versus the patient source documentation (records), eCRF, and drug dispensing log.

After this check, and after the sponsor has granted written approval of destruction, empty or partially used vials should be destroyed at the study site following local policies. The destruction must be documented.

For their home treatment, sufficient amount of Octanorm will be handed out to the patients. The Investigator or his designee has to document the date, quantities and batch (lot) number(s) of IMP handed out including the corresponding patient number. The patients will be advised to return used or expired vials to the study site at their on-site visits and the (early) Termination Visit.

5.7.2 Assessment of Treatment Compliance

Patients will receive infusions at the study site and at home (administered at home by the patient or his/her relative or caregiver). Infusion details will be documented together with the batch number(s) in the eCRF.

Throughout the study, patients will be asked to document on a diary the date, batch (lot) numbers, number of vials, speed of infusion, injection site(s), occurrence of infections, TEAEs and local tissue reactions at injection sites, missed days from work/school/kindergarten/day care, inpatient hospital stays, and any changes in concomitant therapy between visits. The diary will be reviewed during the patient's infusion visit at the study site.

6 STUDY CONDUCT

6.1 Observations by Visit

6.1.1 Screening Visit

The Screening (First) Visit will in most cases be the same as the last study visit (Termination Visit scheduled in week 65, the End-of-study visit) of the main study SCGAM-01 (since most patients will migrate directly from the main study SCGAM-01 to the present extension study; Section 3.2). Screening procedures are to be conducted *before* the IMP administration for that visit.

If the treatment with Octanorm was interrupted between the SCGAM-01 and extension (SCGAM-03) studies (for details see Section 3.2), then all screening procedures (see study flow chart) are to be conducted at the new Screening visit.

Study-related procedures will begin only after written informed consent has been obtained by the patient or their legal guardian. At the Screening Visit the following activities will be performed (as stated above, these need NOT be duplicated at a single visit):

- Written informed consent.
- Check of inclusion and exclusion criteria.
- Documentation of medical history including all adverse conditions that have occurred after the end of the SCGAM-01 study.
- Recording of all previous drug and non-drug therapies administered after the end of the SCGAM-01 study.
- General physical examination, including body weight and vital signs.
- Drawing of blood samples for total IgG trough level.
- Drawing of blood samples for safety laboratory parameters including viral markers.
- Urine sampling including urine pregnancy test (in females of childbearing potential only).
- Infusion of Octanorm
- Check for injection-site reaction and assessment if necessary
- Issue of patient's diary
- Completion of QoL questionnaire.
- Recording of any concomitant medication and adverse events (only new ones, not previously recorded in the SCGAM-01).

6.1.2 Treatment and Assessment Visits

Each patient who stays in the study for the whole period may receive up to 234 weekly infusions of Octanorm (or less, if infused bi-weekly). On study visit days, administration will be performed on site; otherwise, at home (Section 3.3.2).

At the study visits, the following activities will be performed *before* IMP administration:

- General physical examination, including body weight and vital signs (every visit).
- Drawing of blood samples for total IgG trough level (every visit).
- Drawing of blood samples for safety laboratory parameters (Week 12 Visit, every 24-weeks at scheduled study visits following the Week 12 Visit, and the Final Infusion Visit).
- Drawing of blood samples for viral markers (Week 60 Visit and the Termination Visit).
- Urine sampling including urine pregnancy test (in females of childbearing potential only; Week 12 Visit, every 24-weeks at scheduled study visits following the Week 12 Visit, and the Final Infusion Visit).

During or after IMP administration:

- Completion of QoL questionnaire (Week 60 Visit).
- Collection of the patient diary. The Investigator will review the diary entries and will ask the patient about any AEs that may have occurred and any changes in concomitant therapies (medication and non-drug therapy). Any concomitant medication and adverse events will be recorded. Relevant diary data will be transferred to the eCRF. Discrepancies between patient diary entries and eCRF entries must be explained by the Investigator (every visit).
- Infusion of Octanorm (every visit).
- Check for injection-site reaction and assessment if any reaction is present (every visit).

For laboratory testing please refer to Section 7.3.4.

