
The first study (Screening) visit of SCGAM-03 with the first Octanorm infusion will be the same visit as the visit in Week 65 (End-of-Study Visit) of the study SCGAM-01.
 
Eligible patients who have completed the SCGAM-01 study and were treated with any other commercially available SCIG before the start of the SCGAM-03 study (e.g. owing to a delay in local IRB approval for SCGAM-03) are permitted to enter the SCGAM-03 study.
 
The maximum allowed intermission of IgG treatment after completion of the SCGAM-01 study and before the start of treatment in the SCGAM-03 study is 5 weeks.
 
Patients for whom the Week 65 visit of the SCGAM-01 study is not identical to the First visit of the SCGAM-03 study will undergo a separate Screening visit with relevant screening procedures. Only after the patient's successful Screening and enrolment into SCGAM-03 study will the first infusion of Octanorm be permitted.
 
Screening visit assessments, to be performed before the First infusion, will include: physical examination (including weight); blood sampling for hematology, clinical chemistry, viral markers and trough total IgG, urine sample for urinalysis and urine pregnancy test (females of childbearing potential only), and completion of the same QoL questionnaire as used in the SCGAM-01 study. Note that these examinations will, for most patients, be performed within the framework of the main study SCGAM-01 (End-of-Study Visit in Week 65), in which case they need not be repeated at the same visit for SCGAM-03.
 
Patients will stay at the study site during the infusion, vital signs will be measured just before the start of each infusion given at the study site, then within 1 hour after the end of the infusion.
 
The patient's diary for the coming period of the home treatment will be issued to the patients. Ongoing adverse events and any relevant concomitant medications will be recorded.
 
At all subsequent study visits, the patients will undergo the following examinations at the site before the start of infusion: physical examination (including weight), blood sampling for hematology and trough total IgG, clinical chemistry, urine sample for urinalysis, with a urine pregnancy test if indicated. The patient's diary will be collected and reviewed. Other study assessments will be performed as indicated in the Flow Chart of Study Events.
 
One week after the last infusion, for both regular or premature termination, a termination visit will be performed at the site with the following assessments: physical examination (including vital signs and weight), blood sample for hematology, clinical chemistry, viral markers, and trough total IgG; urine sample for urinalysis and urine pregnancy test (females of childbearing potential only); completion of the QoL questionnaire; collection and review of the patient's diary.
 
AEs and any changes in concomitant medications will be recorded throughout the study period.
	

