6.1.3 Termination Visit

One week after the Final Infusion Visit (after patient withdrawal or study termination by one of the events described in Section 6.2.3), a Termination Visit will be performed including the following assessments:

- General physical examination (including vital signs).
- Drawing of blood samples for safety laboratory parameters including viral markers.
- Drawing of blood samples for total IgG trough level.
- Urine sampling including urine pregnancy test (in females of childbearing potential only).

- Completion of QoL questionnaire.
- Collection and review of the patient diary as at the earlier visits (Section 6.1.2) with recording of any AEs and changes in concomitant medications.
- Assessment of any local infusion-site reactions.

After the final examination, the clinical study is considered completed for the patient. No further study-related assessments may be performed, unless safety concerns (e.g. ongoing AEs) require follow-up.

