## 10. Efficacy Analysis

No confirmatory efficacy analysis will be performed.

The rate of SBI per person-year (bacterial pneumonia, bacteraemia/sepsis, osteomyelitis/septic arthritis, visceral abscess, bacterial meningitis) during the treatment period with octanorm will be presented as point estimates of the rate along with a two-sided 98% CI. Calculation of this CI will account for intra-patient correlation in incidents following a compound Poisson process model. Furthermore, all observed SBIs will be listed individually and in full detail.

In case no serious bacterial infections are observed, it is not possible to calculate a confidence interval with the originally planned method using compound Poisson process model; if this happens, two additional analyses will be presented as sensitivity analyses:

1. The originally planned two sided 98% confidence interval will be calculated for the worse case that one bacterial infections would have been observed.
2. The confidence interval will be calculated using a standard Poisson distribution; this second model will also be used as a sensitivity analysis if a very small number of serious bacterial infections is observed, as within patient correlations are negligible for small number of serious bacterial infections.

The annual rate of all infections of any kind or seriousness will also be presented as point estimate, but along with the two-sided 90% CI. This CI will be calculated using a compound Poisson process model to account for intra-patient correlation in incidents as described above; in addition, and as a sensitivity analysis, the same CI will be calculated using the overdispersed Poisson regression model by means of the SAS procedure GENMOD.

The duration of infection will be summarised by standard descriptive statistics by type of infection and by severity. The individual characteristics of each infection, including the time to resolution will be listed.

The use of antibiotics will be reported as a detailed list of all such medications, and the number of patients treated with antibiotics, the number of treatment episodes and the number of treatment days will be tabulated.

The QoL data will be presented descriptively by visit, along with the change from baseline (i.e. screening visit).

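### Week 60 quality of life is completed during or after the infusion but screening quality of life before it, so the Week 60 change may include a same-day infusion effect

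*Protocol*

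**What the plan says.** Protocol 7.4.2 sets three quality-of-life assessments (screening, Week 60 and termination) but does not place them relative to the infusion. Other parts of the protocol do.

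- **Screening.** The synopsis (Study Procedures) says "Screening visit assessments, to be performed before the First infusion, will include" a list that contains "completion of the same QoL questionnaire as used in the SCGAM-01 study". Section 6.1.1 gives a general rule: "Screening procedures are to be conducted *before* the IMP administration for that visit". The bullet list in that section, however, prints the questionnaire after the infusion, the injection-site check and the issue of the diary.
- **Week 60.** Section 6.1.2 has one list of activities before administration and a second list headed "During or after IMP administration". The questionnaire is absent from the first list and is the first item of the second: "Completion of QoL questionnaire (Week 60 Visit)".
- **Termination.** Section 6.1.3 places this visit "One week after the Final Infusion Visit", and the flow chart marks no on-site infusion for it.
- **Flow chart.** Footnote 3 marks procedures done before administration. It is attached to weight, physical examination and the laboratory rows, but not to the quality-of-life row.
- **Analysis.** SAP section 10 states: "The QoL data will be presented descriptively by visit, along with the change from baseline (i.e. screening visit)". Protocol 9.2.2 plans the same and defines baseline as the first infusion. Neither mentions when the form is completed relative to an infusion.

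**The concern.** A change score is easiest to interpret when the instrument is given in the same circumstances at both ends. Here the baseline form is to be completed before any infusion at that visit, while the Week 60 form is to be completed with the infusion running or just finished.

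The documents make a same-day effect plausible. Protocol 5.5 allows up to 6 simultaneous sites and up to 60 mL per site. Section 7.3.2 treats local swelling from the infused volume and brief puncture pain as expected in every patient. Section 1.1 describes local reactions as common, with reported rates of 0.028 to 0.697 per infusion in the cited review.

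The effect on quality of life is the first-listed secondary objective. The study has one arm, so no comparator would cancel an effect of setting. Week 60 is also the only fixed on-treatment assessment, because the date of termination depends on entry date, withdrawal and study end. If the setting shifts the score, the planned tables cannot separate that shift from a real change.

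**Working it through.** The plan states no effect size, standard deviation or power for quality of life, so there is no figure to reproduce. The check compares the timing at the three visits and follows it through the planned change scores.

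1. **Notation.** Let S, W and T be the scores that a patient would give at screening, Week 60 and termination with no infusion beforehand at that visit. Let d be the shift, if any, from answering during or after an infusion.

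2. **Timing as the synopsis, the general rule in 6.1.1, and sections 6.1.2 and 6.1.3 set it out.**
   - Screening, before the infusion: observed score = S
   - Week 60, during or after the infusion: observed score = W + d
   - Termination, no infusion: observed score = T

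3. **Planned changes from baseline.**
   - Week 60: (W + d) − S = (W − S) + d
   - Termination: T − S

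   Only the Week 60 change carries d.

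4. **Do screening and termination match in other respects?** For patients who migrate directly, screening is the Week 65 visit of SCGAM-01, about one week after the Week 64 infusion. Termination is one week after the last infusion. On this point the two settings are alike.

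5. **If a site follows the printed order of the 6.1.1 list instead.** The screening score becomes S + d. If d is the same at both visits, the Week 60 change is (W + d) − (S + d) = W − S. The termination change is then T − (S + d) = (T − S) − d. The exposure moves but does not disappear. This order conflicts with the synopsis and with the general rule in 6.1.1.

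6. **Value of d.** Neither document reports an effect of an infusion on SF-36 or CHQ-PF50 scores, and neither gives the recall period of either form. No number or sign can be assigned to d. The Week 60 heading also covers both answering during the infusion and answering after it, so d may differ between patients.

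7. **Who answers.** Patients aged 14 or over at SCGAM-01 entry complete the SF-36 themselves. For younger patients a parent or guardian completes the CHQ-PF50, so the child's discomfort could affect the score only through the adult's report.

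**The case against.** The strongest objection is that the baseline timing is not settled. The 6.1.1 list prints the questionnaire after the infusion. The general rule in that section cannot cover every listed item, because the infusion is one of them. The missing footnote 3 applies to the whole quality-of-life row, screening included. The second heading in 6.1.2 is also loosely drafted, since the infusion itself appears under it. A site following the printed order at screening would have no mismatch with Week 60. This stands as a reason not to call the mismatch certain in practice. It does not remove the point: the synopsis is explicit, the protocol gives sites conflicting instructions, and step 5 above shows that the other order exposes the termination change.

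A reader might infer that all the planned change scores are distorted. The documents do not support that. On the pre-infusion reading, screening and termination match. A Week 60-to-termination contrast would be exposed, but neither document plans one.

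A reader might also infer that Week 60 scores will be worse. That does not follow either. Section 1.1 says local reactions are rarely severe and accepted by most patients, entry required good tolerance of the product in SCGAM-01, and nothing links reactions to questionnaire scores.

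Finally, correction comes late. Enrolment began in the second quarter of 2016, and 60 weeks is 60 × 7 = 420 days, about 14 months. The earliest patients therefore reached Week 60 at about June to August 2017, before the October 2018 protocol and the July 2019 SAP. Moving the item now may leave Week 60 forms with mixed timing. That is a real cost, and the reason for flagging the forms.

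**Conclusion.** The point holds in a limited form. The written timing differs between screening and Week 60, and neither document acknowledges it, so the planned screening-to-Week 60 change may include a same-day infusion effect. Its size and direction are unknown, it may be zero, and for the CHQ-PF50 it would be indirect. The screening-to-termination change is not exposed.

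This conclusion assumes that sites complete the screening form before the infusion, as the synopsis says, and the Week 60 form where 6.1.2 lists it. The Canadian protocol that the SAP also covers is not among the documents, so timing at Canadian sites cannot be checked.

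The issue is minor. Quality of life is a secondary outcome reported descriptively, by visit as well as by change, and no test, decision rule or safety conclusion depends on it. It is worth correcting because the correction is small and removes an avoidable difference in setting.

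**What to change.** - In protocol 6.1.2, move the Week 60 questionnaire to the list of activities before administration.
- In the flow chart, add footnote 3 to the quality-of-life row.
- In protocol 6.1.1, reorder the list so that the questionnaire comes before the infusion, in line with the synopsis. It then precedes any infusion at every visit.
- In SAP section 10, state that Week 60 forms completed during or after the infusion will be flagged where site records show the timing. Where they do not, report the timing difference as a limitation of the Week 60 change. The protocol does not require the completion time to be recorded, so the limitation statement may be all that is possible for many forms.

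The cost is two moved items, one footnote and a sentence or two in the SAP. No extra visit, instrument or staff is needed. The downside is that Week 60 forms may have mixed timing across protocol versions, which the flag or the limitation should make visible.

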6.1.3 Termination Visit

One week after the Final Infusion Visit (after patient withdrawal or study termination by one of the events described in Section 6.2.3), a Termination Visit will be performed including the following assessments:

- General physical examination (including vital signs).
- Drawing of blood samples for safety laboratory parameters including viral markers.
- Drawing of blood samples for total IgG trough level.
- Urine sampling including urine pregnancy test (in females of childbearing potential only).

- Completion of QoL questionnaire.
- Collection and review of the patient diary as at the earlier visits (Section 6.1.2) with recording of any AEs and changes in concomitant medications.
- Assessment of any local infusion-site reactions.

After the final examination, the clinical study is considered completed for the patient. No further study-related assessments may be performed, unless safety concerns (e.g. ongoing AEs) require follow-up.

6.1.4 Interpretation of Time Windows in This Study

For this study the following time windows apply (see Table 3):

Table 3: Time Windows Used in this Study

Time point	Time stated	Tolerance
On site Visits beginning with Week 12	Weeks 12, 24, 36, 48, 60, and each subsequent 12 week visit.	± 2 weeks
Interval between Last Treatment Visit and (early) Termination Visit	1 week	± 5 days
Blood and urine sampling	before IMP administration	-1 day
Octanorm infusions at patient's home	every week (= every 7 days) or bi-weekly (= every 14 days) at double the weekly dose	±2 days ±2 days

6.2 Duration of Study

6.2.1 Planned Duration for an Individual Patient

Patients will receive weekly (or bi-weekly) infusions until Octanorm becomes commercially available in the USA, or the Sponsor decides to terminate the study, or December 2020 (whichever comes first). The total number of infusions will vary for each patient based on the date the patient entered into Study SCGAM-03.

6.2.2 Planned Duration for the Study as a Whole

The study started enrolling in the second quarter of 2016. Completion of the study by the last patient is expected in December 2020, giving total study duration of approximately 4.5 years.

This duration may be shorter if the sponsor decides to end the trial earlier, or when Octanorm becomes commercially available in the USA (for details see Section 3.2).

6.2.3 Premature Termination of the Study

Both the responsible Investigators and the Sponsor reserve the right to terminate the study at any time. Should this be necessary, the procedures will be arranged on an individual study basis after review and consultation by both parties. In terminating the study, the Sponsor and the Investigator will ensure that adequate consideration is given to the protection of the

patients' interests. Premature termination will be notified in accordance with applicable regulatory requirements.

Furthermore, the Investigator should promptly inform the IRB and provide a detailed written explanation. The pertinent regulatory authorities and IRBs are to be informed according to national regulations.

Early termination of the study as a whole or center-wise may apply for the following reasons:

Clinical Study:

- At any time the study as a whole will be terminated prematurely if e.g.:
 - New toxicological or pharmacological findings or safety reports invalidate the earlier positive benefit-risk-assessment.
 - If more than 2 TEEs (i.e. ischemic stroke, transient ischemic attack, cerebral infarction, cerebrovascular accident, cerebral thrombosis, embolic infarctions, [acute] myocardial infarction, deep vein thrombosis, pulmonary embolism, venous thrombosis excluding thrombophlebitis) are observed fulfilling the following criteria:
 - assessed as probably or possibly related to Octanorm treatment by Investigator and/or Sponsor;
 - confirmed by the Independent Data Monitoring Committee (IDMC).
 - Any other reason rendering the continuation of the study impossible for the Sponsor.

Study Center:

- At any time the study can be terminated at an individual center if e.g.:
 - The center cannot comply with the requirements of the protocol.
 - The center cannot comply with applicable standards.
 - The required recruitment rate is not met.

Should the study be prematurely terminated, all study materials (completed, partially completed and blank forms, IMP, etc.) must be returned to the Sponsor.

